5.2 Primary Efficacy Analyses

The analyses on the primary efficacy variables will be performed on both the mITT and the PP populations. Comparisons will be made between each of the BOTOX[®] dose levels and placebo without multiplicity adjustment.

5.2.1 Primary Analyses of Primary Efficacy Variable(s)

The primary null hypothesis is that at week 12 the difference in mean change from baseline in logarithm value of the geometric mean IELT between BOTOX[®] and placebo is at zero, and there is no dose response shown in the change from baseline in logarithm value of the geometric mean IELT.

To test the primary null hypothesis, the primary efficacy variable in relation to dose levels will be analyzed using an ANCOVA model with treatment as the fixed effect and baseline logarithm value in geometric mean IELT as the covariate to assess the relationship of response across the BOTOX[®] dose levels. Comparisons of the LSMEANS from the ANCOVA model will be made for each of the active BOTOX[®] dose levels vs. placebo. Coefficient of variation (CV) will be presented for the geometric IELT, and the LSMEAN and its 95% confidence interval (CI) as well as treatment difference in LSMEAN and its 95% CI for each active BOTOX[®] dose level vs. placebo will be back-transformed to original unit (seconds) to facilitate review.

The same ANCOVA model using the PP population will be performed.

To assess the dose-response of the active treatment, a linear regression model with baseline logarithm value in geometric mean IELT and dose level (numeric value) as the independent variables and the primary efficacy variable as the dependent variable in the model will be conducted at week 12. The same analysis will also be carried out for the PP population.

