7.5 Sample Size Calculation

For this exploratory study, an empirical sample size is used. For Cohorts 1-5, 8 patients will be randomized to receive BOTOX and 2 patients to placebo. In Cohort 6, 24 patients will be randomized in a 1:1 ratio. The power for detecting 2, 3 and 4-fold change (the ratio between groups) with differing values for the coefficient of variation (CV) assuming the IELT is log-normally distributed, using a 2-group t-test with a 1-sided 0.10 significance level are presented in Table 7–1. The CV assumption is estimated from the pooled analysis of week 12 data from Priligy (dapoxetine hydrochloride) film-coated tablets, 30 and 60 mg (Public Assessment Report Scientific Discussion of Priligy, 2008) (Table 7–2). The CV in the pivotal studies at week 12 ranges from 0.85 to 1.64. The commercial Guide 5.1 (procedure

Table 7–1 Power Calculation with Different Expected Fold-change Comparison Ratio and Coefficient of Variations

	BOTOX versus		
Expected Fold-change	Placebo	Coefficient of Variation	Power
		1	38%
2	8 versus 2	1.5	30%
		2	26%
	8 versus 8	1	63%
2		1.5	48%
		2	41%
		1	61%
3	8 versus 2	1.5	47%
		2	40%
3	8 versus 8	1	89%
		1.5	75%
		2	65%
4		1	76%
	8 versus 2	1.5	59%
		2	51%
4	8 versus 8	1	97%
		1.5	88%
		2	79%
		1	76%
2	12 versus 12	1.5	60%
		2	51%
		1	97%
3	12 versus 12	1.5	88%
		2	79%
		1	>99%
4	12 versus 12	1.5	96%
		2	91%

Table 7–2 Coefficient of Variation at Week 12 in Priligy Pivotal Studies

Study	Treatment Group	Mean (SD)	Coefficient of Variation
C-20052-012	Placebo	1.7 (2.09)	1.23
	DPX 30 mg PRN	2.9 (3.59)	1.24
	DPX 60mg PRN	3.4 (3.97)	1.17
C-2002-013	Placebo	1.8 (2.33)	1.29
	DPX 30 mg PRN	2.7 (3.39)	1.26
	DPX 60mg PRN	3.3 (3.40)	1.03
PRE-3001	Placebo	1.9 (3.11)	1.64
	DPX 30 mg PRN	3.2 (4.61)	1.44
	DPX 60mg PRN	3.5 (4.04)	1.15
PRE-3003	Placebo	2.4 (2.05)	0.85
	DPX 30 mg PRN	3.9 (3.95)	1.01
	DPX 60mg PRN	4.2 (3.97)	0.95
Pooled	Placebo	1.9 (2.43)	1.28
	DPX 30 mg PRN	3.1 (3.91)	1.26
	DPX 60mg PRN	3.6 (3.85)	1.07

DPX = dapoxetine hydrochloride; PRN = as needed; SD = standard deviation

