2.3 Data Conventions

- A one-sided, alpha=0.1 significance level will be used for this study for treatment comparisons, i.e., treatment differences are considered significant if the 1-sided p-value of the test used in the comparison is less than or equal to 0.1.
- Data will be pooled across centers in all analyses. Placebo patients from different cohorts will also be pooled to form the placebo treatment group in all analyses.
- Day 1 is defined as the day of the first study medication administration. Study day is calculated as: Study day=visit date-day 1 date +1 for visits occurred after day 1 and study=visit date -day 1 date for visits occurred before day 1.
- The Medical Dictionary for Regulatory Activities (MedDRA) will be used to code all adverse events and medical history.
- Medications will be coded by the World Health Organization Drug Dictionary Enhanced (WHO DDE) preferred name for the medication's name and MedDRA for the medication's indication.
- All adverse events/medications with missing onset/stop dates will be identified and the missing dates will be imputed as follows:
 - a) For adverse event onset date: if day and month are missing but year is available then the imputed date would be January 1st of that year, or day 1 if they are in the same year. If day is missing but month and year are available then the imputed day will be the first day of the month or day 1 if they are in the same month and year.
 - b) For adverse event stop date: if day and month are missing but year is available then the imputed day will be December 31st of that year, or the study exit date if they are in the same year. If only day is missing but moth and year are available then the imputed day will be the last day of the month of the year, or the study exit date if they are in the same month and year.

- Data from unscheduled/re-test visits, excluding lab data, will also be treated the same way as scheduled visits, i.e., put in the visit window and decided by the visit day's distance to target day as which one to be used in the analyses.
- Weight and height will be presented with the metric system units and laboratory data will be presented with the Standard International (SI) units.
- Summary statistics for continuous/ordinal data include sample size (N), mean, standard deviation, minimum, median, and maximum and that for categorical data include sample size (N), frequency count and percentage.

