4.5 Past Medical History

Medical history with onset dates prior to the informed consent date will be tabulated and presented for each treatment group and overall. Medical history will be coded using MedDRA primary system organ class (SOC). All medical history will be presented by

treatment group and overall. No statistical comparisons will be performed. A patient-level listing of medical and surgical histories will also be provided for each treatment group.

Patients are also asked to fill out a sexual history CRF which will record their PE therapy or techniques together with start/stop date information. The un-coded therapy/technique will be tabulated with number and percent of patients using each therapy/technique by treatment group and overall. A patient-level listing of the information collected will also be presented.

5. Efficacy Analyses

5.1 Collection of Primary Efficacy Measurement(s) and Derivation of Primary Efficacy Variable(s)

The primary efficacy measurement is the patient's IELT (second) collected from the Sex Intercourse Diary (SID). The SID will be completed by the patient and/or their female partner after any vaginal sexual activity during the screening visit and for 12 or 24 weeks following study treatment. Only IELTs from evaluable events recorded in the SID will be used for analyses.

An evaluable event is defined as:

• An event in which the patient and his partner had vaginal intercourse, and the couple have recorded that the ejaculation occurred "intravaginally" and duration of the time from penetration to ejaculation has been recorded

OR

• An event in which the patient and his partner attempted to have vaginal intercourse. However, the couple have recorded that ejaculation occurred "prior to vaginal penetration". In this scenario, the duration of time will be recorded as zero.

Any other scenarios will not be considered as evaluable and will not be included in deriving the primary efficacy variable, although time to withdrawal can be used in exploratory analyses. Number of evaluable events will be summarized by treatment group at baseline, weeks 2, 4, 8 and 12 for the randomized period of the study.

The primary efficacy variable is the change from baseline in logarithm value of the individual patient's geometric mean IELT for the entire 12 weeks of the randomized period of the study.

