For baseline, the geometric mean IELT is calculated from the most 4 recent evaluable events prior to study medication administration. The geometric mean of the IELTs from all postbaseline evaluable events up to week 12 is then calculated and the difference in the logarithm of the two geometric mean IELTs (postbaseline - baseline) will be calculated.

For IELTs that are zero (events in which ejaculation occurred prior to vaginal penetration), 0.5 (second) will be added for the calculation of geometric means.

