5.2.2 Other Analyses of Primary Efficacy Variable(s)

As a sensitivity analysis to the log-normal assumption of the geometric mean IELT, Wilcoxon rank-sum test will be performed on the primary efficacy variable for the treatment difference for each of the active BOTOX[®] dose level vs. placebo.

In addition, responder analyses for the primary efficacy variable will also be performed. As treatment responder in PE are defined as 3-8 fold changes in geometric mean IELT, corresponding responders will be defined in the logarithmic value of a 3, 4, 5, 6, 7 and 8 fold

change (1.10, 1.39, 1.61, 1.79, 1.95, and 2.08, respectively) for the primary efficacy variable and the Pearson's chi-squared test will be used to compare the proportion of responders between each of the active BOTOX[®] dose group vs. placebo.

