5.3.1 Secondary Efficacy Analysis

Summary statistics will be provided for each of the secondary efficacy variables. Change from baseline in log-transformed geometric mean IELTs and change from baseline in average mean IELTs will also be calculated and summarized.

Same ANCOVA model used in Section 5.2.1 will be used to the change from baseline in the log-transformed geometric mean IELT up to weeks 2, 4, 6, 8, and 10, respectively as well as change from baseline in interval-based log-transformed geometric mean IELT for weeks 4, 8

and 12, with treatment as the fixed effect, and log-transformed baseline geometric mean IELT as the covariate.

Summary statistics will be provided for average IELT as well as change from baseline in average IELT by timepoint. A similar ANCOVA model will be used on change from baseline in average IELT as well as the interval-based average IELTs: the model will have treatment as the fixed effect and the baseline average IELT as the covariate. Change from baseline in average IELTs up to weeks 2, 4, 6, 8, 10 and 12 and the interval-based change from baseline in average IELT for weeks 4, 8 and 12 will not be log-transformed prior to analyses.

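### SAP 5.2.1 reports the BOTOX–placebo difference and its CI in seconds, but back-transforming a difference in log-change gives a unitless ratio with null value 1

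*SAP*

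**What the plan says.** SAP 5.1 records each IELT in seconds and then moves to a log scale. "The primary efficacy variable is the change from baseline in logarithm value of the individual" patient's geometric mean IELT over the 12-week randomized period. The derivation is explicit: "the difference in the logarithm of the two geometric mean IELTs (postbaseline - baseline) will be calculated".

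SAP 5.2.1 fits an ANCOVA to this variable, with treatment as fixed effect and baseline log geometric mean IELT as covariate, and compares each dose with placebo. It states that each LSMEAN with its 95% CI, and each treatment difference in LSMEAN with its 95% CI, "will be back-transformed to original unit (seconds) to facilitate review". It gives no formula. Protocol 7.3.1 gives no back-transformation and leaves details to the SAP.

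Elsewhere the plan treats this scale as a fold-change scale. In SAP 5.2.2, "corresponding responders will be defined in the logarithmic value of a 3, 4, 5, 6, 7 and 8 fold" change, and protocol 7.5 describes the effect to be detected as a ratio between groups.

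**The concern.** A difference between two logarithms back-transforms to a ratio. The BOTOX–placebo contrast is a difference of differences of logs, so seconds cancel within the patient and nothing brings them back. A result labelled in seconds would mislead a reader in two ways:

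- **Size.** A ratio of 2 would be read as a gain of 2 seconds, whatever the baseline.
- **Null value.** A difference in seconds is judged against 0, a ratio against 1. An exponentiated CI is always above 0, so every comparison would seem to exclude no difference, including results that favour placebo.

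This is the prespecified primary estimate of a pilot study whose data, according to protocol 1.5, will help design later trials.

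**Working it through.** **1. Fix the scale from the plan's own figures.** For each patient, Y = ln(G_post) − ln(G_base) = ln(G_post / G_base).

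- SAP 5.2.2 gives cut-offs on Y of 1.10, 1.39, 1.61, 1.79, 1.95 and 2.08 for 3- to 8-fold change. These equal ln 3 to ln 8 to two decimals, all six. Y is therefore the natural log of a ratio.
- Protocol Table 7–1 was recomputed with a two-group noncentral t, effect ln(ratio), SD = √ln(1 + CV²) and 1-sided alpha 0.10. All 27 cells reproduce within 1 percentage point. Examples: 8 versus 8, 2-fold, CV 1: 63.1% against the stated 63%; 12 versus 12, 3-fold, CV 1.5: 87.5% against 88%.

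**2. Back-transform.** Let L_B and L_P be the LSMEANs of Y, D = L_B − L_P, and b the mean baseline log IELT.

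- exp(D) is the fold-change on BOTOX divided by the fold-change on placebo. It is unitless, and the null D = 0 becomes exp(0) = 1.
- exp(L_B) and exp(L_P) are fold-changes from baseline, also unitless.
- exp(b + L_B) and exp(b + L_P) are in seconds. In the contrast b cancels: (b + L_B) − (b + L_P) = D. Adding the baseline back rescues the arm-level values but not the difference.

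**3. Numerical check.** One simulated data set (12 versus 12, assumed baseline near 30 s) was fitted in seconds and again in minutes. A quantity in seconds must change 60-fold.

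- exp(D) was 2.813 (95% CI 1.312 to 6.032) in both fits.
- exp(L_P) and exp(L_B) were 1.033 and 2.906 in both fits.
- Multiplying by the baseline geometric mean of 31.79 s gave 32.84 s and 92.38 s. Their difference is 92.38 − 32.84 = 59.54 s, which is not 2.813.

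**4. Size of the mislabelling.** Difference in seconds = baseline × placebo fold-change × (ratio − 1). Take a ratio of 2, the smallest in Table 7–1. The baselines and placebo fold-changes below are assumptions.

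| Baseline (s) | Placebo fold | Difference (s) | Printed value |
|---|---|---|---|
| 15 | 1.0 | 15 × 1.0 × 1 = 15 | 2.0 |
| 15 | 1.5 | 15 × 1.5 × 1 = 22.5 | 2.0 |
| 60 | 1.5 | 60 × 1.5 × 1 = 90 | 2.0 |
| 60 | 2.0 | 60 × 2.0 × 1 = 120 | 2.0 |

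**5. Null value.** Inputs:

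- 12 BOTOX patients (Cohort 6) and 5 × 2 + 12 = 22 placebo patients, pooled across cohorts under SAP 2.3.
- CVs from protocol 7.5 and Table 7–2: 0.85 and 1.64 as the range, 1.28 for pooled placebo.
- An assumed observed ratio of 1.2.
- df = 74 − 7 − 1 = 66 (six distinct doses assumed, plus placebo, and one covariate), so t(0.975) = 1.997.
- SE = SD × √(1/12 + 1/22); CI = 1.2 × exp(±1.997 × SE).

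| CV | Log SD | SE | Half-width | 95% CI for ratio | 1-sided p |
|---|---|---|---|---|---|
| 0.85 | 0.737 | 0.265 | 0.528 | 0.71 to 2.04 | 0.25 |
| 1.28 | 0.985 | 0.353 | 0.706 | 0.59 to 2.43 | 0.30 |
| 1.64 | 1.143 | 0.410 | 0.819 | 0.53 to 2.72 | 0.33 |

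All three CIs include 1, and none of the p-values meets the SAP 2.3 limit of 0.1. All three CIs nevertheless lie above 0. An assumed ratio of 0.8, which favours placebo, gives 0.39 to 1.62 at CV 1.28, also wholly above 0.

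**The case against.** The strongest reply is that this is a presentation aid in an exploratory study. SAP 2.3 settles significance by p-value: "treatment differences are considered significant if the 1-sided p-value of the test used in the comparison is less than or equal to 0.1". That test is made on the log scale and does not change. Nothing says that the log-scale estimates will be withheld, so a reader is misled only if the programmer exponentiates directly, keeps the seconds label and the reader then ignores the p-value.

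Arm-level values in seconds are also legitimate. With baseline log IELT as covariate, modelling the log-change gives the same treatment difference as modelling the log post-treatment value, and the LSMEANs differ only by the constant b. SAP 5.3.1 reuses the model ("Same ANCOVA model used in Section 5.2.1 will be used to the change from baseline in the log-transformed geometric mean IELT") but announces no back-transformation of its own. The illustrations rest on assumed inputs.

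Most of this stands as a limit on the point. The inference is safe, the LSMEAN part is an unstated step and no more, and SAP 5.3.1 is affected only if its log-scale results are back-transformed in the same way. It does not rescue the difference and its CI. The constant b cancels there, and neither document supplies a method for a difference in seconds. A CI for such a difference is not the back-transformed log CI.

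**Conclusion.** The point holds. For the treatment difference and its 95% CI, the seconds label in SAP 5.2.1 is wrong: the quantity is a BOTOX/placebo ratio with null value 1. For the LSMEANs, the step needed to reach seconds is missing. This follows from the SAP's own definitions and needs no assumption.

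The consequence is confined to reporting. The hypothesis test, p-values, log-scale CIs, responder cut-offs and power are sound. The unit, size and null value of the primary estimate are not, so this should be corrected before tables are produced.

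The size figures are illustrations. They depend on the assumed baselines, placebo fold-changes and observed ratios, on planned enrolment with every patient analysed, and on six distinct doses (the doses are redacted). The CVs are for week-12 IELT in the cited dapoxetine studies and ignore any gain from the covariate. That an exponentiated CI always lies above 0 depends on none of these.

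**What to change.** Amend SAP 5.2.1, and apply the same wording to any back-transformed output from the log-scale models in SAP 5.3.1:

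- Report exp(LSMEAN) with its 95% CI as the geometric-mean fold-change from baseline, unitless.
- Report exp(LSMEAN difference) with its 95% CI as the BOTOX/placebo ratio, unitless, and state that the null value is 1.
- If seconds are wanted, report a baseline-adjusted geometric mean for each arm as exp(mean baseline log IELT + LSMEAN).
- Give a difference in seconds only with a prespecified CI method, such as the delta method or a bootstrap.

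The first two items need only SAP and table-shell wording; no data, test or sample size changes. The outputs in seconds are optional: the arm-level values need a little extra programming, and a difference also needs the CI method specified.

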5.2.2 Other Analyses of Primary Efficacy Variable(s)

As a sensitivity analysis to the log-normal assumption of the geometric mean IELT, Wilcoxon rank-sum test will be performed on the primary efficacy variable for the treatment difference for each of the active BOTOX[®] dose level vs. placebo.

In addition, responder analyses for the primary efficacy variable will also be performed. As treatment responder in PE are defined as 3-8 fold changes in geometric mean IELT, corresponding responders will be defined in the logarithmic value of a 3, 4, 5, 6, 7 and 8 fold

change (1.10, 1.39, 1.61, 1.79, 1.95, and 2.08, respectively) for the primary efficacy variable and the Pearson's chi-squared test will be used to compare the proportion of responders between each of the active BOTOX[®] dose group vs. placebo.

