2.2 Clinical Hypotheses

BOTOX injected bilaterally into the bulbospongiosus muscle has an acceptable safety profile and shows an efficacy signal in comparison to placebo, as demonstrated by an increased IELT.

3. Study Design

This is a phase 2a, multicenter, randomized, double-blind, placebo-controlled, single treatment, pilot study followed by an open-label observation period, to assess a range of BOTOX doses for the treatment of male patients with PE. Patients will attend a minimum of 6 or 7 clinic visits and also have 1 or 2 telephone visits in the randomized period: screening, day 1 (treatment), day 2 (telephone visit for non-sentinel patients, clinic visit for sentinel patients, week 1 (telephone visit, and weeks 2, 4, 8, and 12/study exit). Partners will need to either attend a clinic visit or participate on a video conference during the screening period to provide informed consent and to receive training on measurement and recording of the IELT. For the open-label period, patients will have 2 clinic visits (weeks 4 and 12/study exit), along with 3 telephone visits (day 2, weeks 2, and 8).

For Cohorts 1-5, patients will be enrolled in cohorts of 10 patients. Within each cohort, 8 patients will receive BOTOX and 2 patients will receive placebo. For Cohort 6, patients will be enrolled into the randomized period in a 1:1 ratio, with 12 patients receiving BOTOX and 12 patients receiving placebo. Cohort 6 patients may choose to participate in the open-label period where they will receive BOTOX. For each treatment, patients will receive one injection of study medication delivered by ultrasound guidance bilaterally to the bulbospongiosus muscle.

Table 3–1 shows the planned dose escalation scheme; although, other interim doses may be recommended for investigation by the independent Data Review Committee (DRC) following data review.

Cohort	Total Dose	Sample Size	Total Patients in Cohort
1		N = 8	10
1	Placebo	N=2	10
2		N = 8	10
2	Placebo	N = 2	10
3		N = 8	10
	Placebo	N = 2	10
4		N = 8	10
	Placebo	N = 2	10
5		N = 8	10
	Placebo	N=2	10
6		N = 12	24
	Placebo	N = 12	24

Table 3–1 Planned Dose Escalation Scheme

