- Change from baseline is calculated as follow-up minus baseline, and treatment difference will be calculated as BOTOX[®] minus placebo.
- The type III sums of squares will be used for all analysis of covariance (ANCOVA) and analysis of variance (ANOVA) models.
- Unless otherwise specified, comparisons on categorical data will be performed using Pearson's Chi-square test. When 25% or more of the cells have expected counts of less 5, Fisher's exact test will be used.
- Except for AE and medication onset/stop dates, missing data will not be imputed.

3. Disposition and Exit Status

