5.4 Other Analyses of Secondary Efficacy Variables

Nonparametric analysis using the Wilcoxon rank-sum test will be performed on the geometric mean IELT up to weeks 2, 4, 6, 8 and 10 as well as interval-based geometric mean IELT for weeks 4, 8 and 12, to compare each active BOTOX[®] dose level vs. placebo. Responder analyses described in 5.2.2 will also be carried out for geometric mean IELTs up to weeks 2, 4, 6, 8 and 10.

Treatment comparisons of each active BOTOX[®] dose level vs. placebo Geometric mean IELT up to weeks 4, 8 and 12 will also be performed using methods described in Zhou et al, 1997:

1. The likelihood-based Z-score test: the comparison between an active BOTOX[®] dose level *i* and placebo is evaluated by the statistic Z_i :

$$Z_{i} = \frac{\hat{\mu}_{i} - \hat{\mu}_{0} + \frac{1}{2}(S_{i}^{2} - S_{0}^{2})}{\sqrt{\frac{S_{i}^{2}}{n_{i}} + \frac{S_{0}^{2}}{n_{0}} + \frac{1}{2}(\frac{S_{i}^{4}}{n_{i} - 1} + \frac{S_{0}^{4}}{n_{0} - 1})}}$$

Where $\hat{\mu}_i$ and $\hat{\mu}_0$ are the sample mean of the log-transformed geometric mean IELT of dose level *i* and placebo, S_i^2 and S_0^2 are the sample variance of the log-transformed geometric mean IELT of dose level *i* and placebo, and n_i and n_0 are the sample size of dose level *i* and placebo, respectively.

Assuming that for each of the active dose level *i* and placebo, the geometric mean IELT are independently log-normally distributed with means M_i and M_0 , respectively, then Z_i tests the null hypothesis of $M_i=M_0$, and under the null hypothesis Z_i is approximately standard normal.

2. Bootstrap approach:

Let \overline{T}_i , \overline{T}_0 and $\overline{T}^{(i,0)}$ be the sample mean of the geometric mean IELT of the dose level i, placebo and the two groups combined, respectively. $T_k^{(i)} = T_{ik} - \overline{T}_i + \overline{T}^{(i,0)}$ and $T_j^{(0)} = T_{0j} - \overline{T}_0 + \overline{T}^{(i,0)}$ form a sample with common mean $\overline{T}^{(i,0)}$, where T_{ik} and T_{0j} are the geometric mean IELT for the kth patient in dose level i and the jth patient in the placebo group, for k=1, ..., n_i and j=1,..., n_0. Resample from them with replacement 2000 times, $Z_{i1}^{*(b)}$,..., $Z_{in_i}^{*(b)}$ and $Z_{01}^{*(b)}$,..., $Z_{0n_0}^{*(b)}$ for each b=1, ..., 2000. Compute

$$t_{b,i}^* = \frac{\overline{Z}_i^{*(b)} - \overline{Z}_0^{*(b)}}{\sqrt{\frac{\tau_i^{*(b)2}}{n_i} + \frac{\tau_0^{*(b)2}}{n_0}}}, \text{ for b=1,..., 2000.}$$

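### The SAP names Pearson's test for the responder comparisons in 5.2.2 but switches sparse tables to Fisher's in 2.3; it does not say which governs, and at 8 or 12 vs 22 patients the choice matters

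*SAP*

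**What the plan says.** SAP 5.2.2 defines responders by 3-, 4-, 5-, 6-, 7- and 8-fold changes in geometric mean IELT. It then states that "the Pearson's chi-squared test will be used to compare the proportion of responders between each of the active" dose groups and placebo. SAP 5.4 repeats this at earlier times: "Responder analyses described in 5.2.2 will also be carried out for geometric mean IELTs up to weeks 2, 4, 6, 8 and 10".

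SAP 2.3 carries a general rule: "Unless otherwise specified, comparisons on categorical data will be performed using Pearson's Chi-square test". The next sentence adds: "When 25% or more of the cells have expected counts of less 5, Fisher's exact test will be used".

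The level is also in 2.3: "A one-sided, alpha=0.1 significance level will be used for this study for treatment comparisons". The SAP does not say how a one-sided p-value is obtained from a chi-square statistic.

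The arm sizes are in Protocol Section 3 (Study Design). For Cohorts 1-5, "Within each cohort, 8 patients will receive BOTOX and 2 patients will receive placebo"; Cohort 6 is randomised 1:1, "with 12 patients receiving BOTOX and 12 patients receiving placebo". Under SAP 2.3, "Placebo patients from different cohorts will also be pooled to form the placebo treatment group in all analyses".

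**The concern.** The rule in 2.3 opens with an exception for tests specified elsewhere, and 5.2.2 specifies one. A programmer can read 5.2.2 as that exception and run Pearson's throughout. Another can read 5.2.2 as merely naming the default and apply the Fisher fallback. Both would be following the plan.

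At these arm sizes the two readings can give opposite answers on the same data. One uses a test that the SAP's own adequacy rule rejects in every 8-patient comparison. The other uses a test that spends less than half of the stated 10% error in those comparisons. The same uncertainty carries over to the earlier time points in 5.4.

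**Working it through.** **The plan's own figures.** The documents give no error rate or power for the responder test. Protocol Table 7-1 covers a t-test on log IELT, and it reproduces. For 12 vs 12, 2-fold, CV 1: SD = √ln(1+1²) = 0.833, noncentrality = ln 2 / (0.833 × √(1/12+1/12)) = 2.04, one-sided 0.10, power 76.4% (table: 76%). All 27 cells agree within 1 point. The table does not bear on responders.

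**Inputs.** Active arm 8 (Cohorts 1-5) or 12 (Cohort 6). Pooled placebo 5 × 2 + 12 = 22. Level one-sided 0.10. The documents give no responder rates, so those below are assumptions.

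**When the 2.3 switch applies.** With R responders among N men, the smallest expected count is n_active × min(R, N−R)/N.
- 8 vs 22: at most 8 × 15/30 = 4. At least one cell in four (25%) is always below 5, so the switch always applies.
- 12 vs 22: reaching 5 needs min(R, 34−R) ≥ 5 × 34/12 = 14.2, so the switch applies unless R is 15 to 19.

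**Method.** All 2×2 outcomes were enumerated with binomial probabilities.
- Pearson: upper normal tail of z = (p₁−p₀)/√[p(1−p)(1/n₁+1/n₀)], the signed root of chi-square.
- Fisher: upper hypergeometric tail.
- Boschloo: tables ordered by Fisher's p, with the largest rejection region whose probability stays at or below 0.10 for every common rate (grid 0.001-0.999).

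**True one-sided error, nominal 10%**

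| Test | 8 vs 22, maximum | 8 vs 22, rates 10-50% | 12 vs 22, maximum | 12 vs 22, rates 10-50% |
|---|---|---|---|---|
| Pearson (5.2.2) | 13.2% (rate about 5%) | 9.3-12.0% | 16.2% (rate about 4%) | 9.9-11.0% |
| 2.3 rule | 4.8% | 3.0-4.8% | 7.5% | 2.5-7.4% |
| Boschloo | 9.4% | 7.6-9.4% | 9.8% | 6.9-9.5% |

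**Power at 8 vs 22 (%)**

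| Placebo / active rate | Pearson | Fisher (2.3) | Boschloo | Boschloo − Fisher |
|---|---|---|---|---|
| 10 / 40 | 71.2 | 48.1 | 64.5 | 16.4 |
| 10 / 50 | 85.3 | 67.4 | 80.4 | 13.0 |
| 20 / 50 | 62.9 | 43.4 | 59.0 | 15.6 |
| 20 / 60 | 79.1 | 63.6 | 76.9 | 13.3 |
| 30 / 60 | 57.6 | 42.9 | 57.0 | 14.1 |
| 30 / 70 | 75.7 | 62.9 | 75.4 | 12.5 |

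At 12 vs 22 Boschloo's gain over the 2.3 rule in the same six scenarios is about 5 to 10 points.

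**Sensitivity of the gap.**
- Fewer patients, same six scenarios: 8.9-12.6 points at 8 vs 20 and 10.5-14.7 at 7 vs 20.
- Very large effects at 8 vs 22: 3.8 points (10% vs 70%) and 1.1 points (10% vs 80%).
- Two 8-patient cohorts sharing a dose (16 vs 22): the 2.3 rule and Boschloo agree within 2 points.

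**Single results at 8 vs 22.**
- 1/8 vs 0/22: z = 0.125/√[(1/30)(29/30)(1/8+1/22)] = 1.69, Pearson p = 0.046; Fisher p = 8/30 = 0.267; Boschloo p = 0.167.
- 3/8 vs 2/22: Pearson 0.032, Fisher 0.102, Boschloo 0.050.
- Of the 65 tables that Pearson calls significant, 14 are not significant by Fisher.

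**The case against.** **The conflict may be only apparent.** It is natural to read 5.2.2 as naming the default and 2.3 as supplying the fallback; the Protocol Summary also lists Fisher's, Pearson's or Cochran-Mantel-Haenszel methods as suits the data. On that reading 1/8 vs 0/22 is never declared significant. This is a fair reading but not the only one, so a clarifying sentence is still needed. A reader might infer that the plan suffers both an inflated error rate and lost power. It cannot: these belong to alternative readings.

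**Pearson is not badly off in general.** A reader might infer that its error is inflated across the board. For common rates of 10-50% it stays within about 2 points of 10%; the excess lies near 4-6%, which the higher fold thresholds could produce. At 12 vs 22 and rates of 10-50% Pearson is nearer 10% than Boschloo is. This stands.

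**The power gap is not a constant.** It depends on assumed rates, full arms and the comparator. Against Barnard's test, also exact and unconditional, Fisher loses only 1.4-10.3 points in the six scenarios. This stands, so the gap should be quoted only with its conditions.

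**Fisher's is conventional and controls error.** True, and these results come under other analyses of an exploratory study. The primary inference is the ANCOVA, with the dose-response regression beside it. Nothing in the documents makes the responder rates the plan's main clinical reading. The many thresholds and times are unadjusted, so exact calibration of each test matters less. This limits the priority but does not settle which test is to be run.

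**Conclusion.** The point holds as an unresolved choice of test with measurable consequences. If 5.2.2 governs, the error rate is close to nominal at moderate response rates but reaches 13.2% or 16.2% at low ones. If 2.3 governs, it never exceeds 4.8% (8 vs 22) or 7.5% (12 vs 22), and the 8-patient comparisons give up about 12-16 points of power relative to Boschloo's test for placebo rates of 10-30% and differences of 30-40 points.

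This rests on full enrolment, every treated man having baseline and post-baseline IELT, no extra sentinel patients, and no dose shared between cohorts. The doses are redacted, so the last cannot be checked. With one or two patients lost per arm the gap is roughly 9-15 points in those scenarios; it is a few points for very large effects and nearly nil at 16 vs 22. The documents do not support treating 12-16 points as a fixed cost, nor the point as a threat to the primary analysis. Modest priority.

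**What to change.** In SAP 5.2.2, replace the named test with Boschloo's exact unconditional test, one-sided at 0.10 in the direction of more responders on BOTOX, for each dose level against pooled placebo. State there that the Pearson/Fisher switch in 2.3 does not apply to these comparisons. SAP 5.4 inherits the change by its reference to 5.2.2. This also settles how the one-sided p-value is formed.

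Boschloo's test keeps the error at or below 9.4% (8 vs 22) and 9.8% (12 vs 22). It is never less powerful than Fisher's, because its rejection region contains Fisher's.

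The cost is one SAP sentence before database lock, with no extra data or patients. There are three drawbacks. Power is somewhat below that of the oversized Pearson test (65% vs 71% at 10% vs 40% responders, 8 vs 22). The test remains conservative at very low rates (true error 4.1% at a common rate of 5% and 1.0% at 2%, 8 vs 22). It is also less familiar to readers. If the sponsor prefers another test, 5.2.2 should still name it, say whether 2.3 applies, and define its one-sided p-value.
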